Early Adolescent Temperament Questionnaire–Revised^{172–173} completed by youth and parents; scales include inhibitory control and higher-order factors: effortful control, negative affect, affiliativeness, extraversion; good internal consistency.¹⁷³

Go/No Go Task of inhibitory control; youth selectively respond to target stimuli and inhibit responses to equally salient, non-target stimuli. 121,174 Consists of 252 trials: a letter is presented for 500-ms with a fixed, 1,500-ms interstimulus interval. Youth is instructed to press button as quickly as possible for every letter (go stimuli) except X (no go stimuli); 75% "go" trials and 25% "no go" trials; activates dorsolateral prefrontal cortex, ventral prefrontal cortex, and anterior cingulate cortex. 174 Consistent with prior research, 175–176 we will compute an index of inhibitory control: subtract percent correct on highly interfering stimuli ("no go" trials) from percent correct on minimally interfering stimuli ("go" trials). Lower scores indicate better inhibitory control.

TREATMENT CONDITIONS

FAMILY-BASED CM. Family-based CM is rooted in behavioral and cognitive behavioral theories and is designed for delivery in outpatient clinic settings (weekly 50-60 minute sessions). Treatment duration is criterion-based, determined by achievement of substance use goals, but the protocol is typically 5-6 months (20-24 sessions). CM has strong empirical support in the adult SUD treatment literature, ¹⁷⁷ and family-based CM has also proven efficacious for youth SUD. ^{13,178} Moreover, its relative simplicity and low cost ¹⁷⁹ makes family-based CM highly amenable to adoption. The protocol components are listed in Table 3.

Table 3. Family-Based CM Components

Clinical assessment. A semi-structured interview conducted separately with the youth and parent gathers type, frequency, quantity, and administration route of drug use; and data on treatment, medical, and educational history.

Introducing CM. CM is introduced to the youth and parent, and the therapist begins to engage them both in treatment.

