AIM 2: DETERMINE WHETHER PARENT MANAGEMENT SKILLS (DIRECT TARGET) MEDIATE THE EFFECT OF TREATMENT ON YOUTH BEHAVIORAL REGULATION & DEVIANT PEER RELATIONS (INDIRECT TARGETS). In the parallel process model for Aim 2, the *a-path* is identical to that for Aim 1. The "outcome" model is nearly identical, the only difference being that the "outcomes" are indirect targets of treatment, behavioral regulation and peer relations. The b-path coefficient represents the association between the during-treatment slope for parent management and the 9- and 12-months post-treatment levels of behavioral regulation and peer relations.

AIM 3: DETERMINE WHETHER BEHAVIORAL REGULATION & DEVIANT PEER RELATIONS (INDIRECT TARGETS) MEDIATE THE EFFECT OF PARENT MANAGEMENT SKILLS (DIRECT TARGET) ON YOUTH SUBSTANCE USE & BEHAVIOR PROBLEMS (ULTIMATE OUTCOMES). Aim 3 uses the same approach, with one key difference: rather than treatment condition, the initial variable is parent management (the direct target of treatment) and, as such, there are repeated measurements. The *a-path* represents the effect of parent management on behavioral regulation and deviant peer relations. With both measured longitudinally, this takes the form of the during-treatment slope for parent management predicting the during-treatment slope for behavioral regulation and deviant peer relations. Although this could confound timing and sequencing of a-path effects, the results of Aim 2 will have established the extent to which there is evidence supporting a causal association between the direct and indirect targets of treatment. The outcome model is identical to that for Aim 1. The *b-path*, holding constant the effect of parent management, is the effect of the during-treatment slopes for behavioral regulation and peer relations on the post-treatment levels of substance use and behavior problems.

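### The Go/No-Go index counts missed go responses as better inhibitory control, and the plan has no check that go accuracy is high enough for the index to work

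*Combined protocol and SAP*

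**What the plan says.** The task is described in Table 2, under Behavioral Regulation - Inhibitory Control. Its format is given as: "Consists of 252 trials: a letter is presented for 500-ms with a fixed, 1,500-ms interstimulus interval". Three quarters of the trials are go trials and one quarter no-go. Youth press for every letter except X, so a go trial is correct when the youth presses and a no-go trial is correct when the youth withholds.

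The scoring rule is to "subtract percent correct on highly interfering stimuli" (the no-go trials) from percent correct on the go trials. The direction is then fixed: "Lower scores indicate better inhibitory control". The text says this follows earlier research and cites two studies.

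The indirect targets are scheduled at months 0, 2, 4, 6, 9 and 12. Under Evaluation of Specific Aims, behavioral regulation is an outcome in Aim 2, as levels at 9 and 12 months, and a mediator in Aim 3, as the during-treatment slope.

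The documents give no minimum go accuracy, no rule for omission errors, no validity exclusion for this task and no separate analysis of commission errors.

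**The concern.** Not responding has two effects on this index. On a go trial it is an error, which lowers the first term. On a no-go trial it is a correct answer, which raises the term being subtracted. Both push the score down, which the plan reads as better inhibitory control. A youth who stops responding can therefore look like one who has learned to hold back.

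The index is sound when almost every go trial is answered, because a high score then reflects false presses to X. It loses that meaning as go accuracy falls, and the plan has no step that would detect the fall. The stake is the meaning of one of the two inhibitory-control measures, which feeds an Aim 2 outcome and an Aim 3 mediator.

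**Working it through.** **Inputs from Table 2.** 252 trials, so 0.75 × 252 = 189 go and 0.25 × 252 = 63 no-go. Index = % correct go - % correct no-go; lower is better. The plan states no numerical result to reproduce, so the check is arithmetic on this definition.

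**Value of one error.** A missed go trial changes the index by -100/189 = -0.53 points (better). A false press on a no-go trial changes it by +100/63 = +1.59 points (worse).

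**Fixed points.**
- Perfect: 100 - 100 = 0.
- Never presses: 0 - 100 = -100, the lowest possible score.
- Always presses: 100 - 0 = +100.
- Presses at random with probability p: 100p - 100(1 - p) = 100(2p - 1). At p = 0.5 this is 0, tied with perfect; at p = 0.3 it is -40; at p = 0.7 it is +40.
- 70% go and 70% no-go: 0, which beats 98% and 80%, at 18.

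The index is below 0, and so better than perfect, whenever go accuracy is below no-go accuracy.

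**Lapses.** The accuracy profiles and lapse rates here are assumptions. Take a youth at 98% go and 80% no-go, with a lapse on a share q of all trials.
- Each lapse is an omission: go = 0.98(1 - q), no-go = 0.80(1 - q) + q, index = 18 - 118q.
- Each lapse is a habitual press: go = 0.98(1 - q) + q, no-go = 0.80(1 - q), index = 18 + 82q.

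| q | Index, omissions | Index, habitual presses |
|---|---|---|
| 0 | 18.0 | 18.0 |
| 10% | 6.2 | 26.2 |
| 15% | 0.3 | 30.3 |
| 30% | -17.4 | 42.6 |

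With omissions, the score passes below perfect when q exceeds d/(1 + d), where d is go minus no-go accuracy as a proportion. For 98/80 this is 0.18/1.18 = 15.3%; for 98/85 it is 0.13/1.13 = 11.5%; for 95/60 it is 0.35/1.35 = 25.9%.

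**Does d-prime avoid the problem?** d-prime = z(go hit rate) - z(no-go false-alarm rate), where z is the standard normal quantile; higher is better. For the 98/80 youth at q = 0 it is z(0.98) - z(0.20) = 2.90. At q = 30% with omissions it is z(0.686) - z(0.14) = 1.57. At q = 30% with habitual presses it is z(0.986) - z(0.44) = 2.35. Both kinds of lapse lower it. Random pressing at any rate gives 0.

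Never pressing needs a correction for zero rates. Adding 0.5 to each count and 1 to each trial total gives z(0.5/190) - z(0.5/64) = -0.37, against z(189.5/190) - z(0.5/64) = 5.21 for perfect performance.

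**Does the commission-error rate avoid it?** No. Never pressing gives 0%, the best possible value, and under omission lapses the rate is 20(1 - q)%, which also improves with q.

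**The case against.** Several points on the other side are fair.

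- **Lapse type.** Youth are told to respond fast and three quarters of trials call for a press, so a lapse may well be a habitual press. That worsens the score, and one false press costs three times what one omission gains. This stands: a reader might infer that inattentive youth in general score best, but only complete non-response reaches the minimum, and the documents do not say which lapses to expect.
- **Effect on the aims.** A reader might also infer that both aims are biased. The documents do not support this. The Aim 2 b-path uses regulation levels at 9 and 12 months; the regulation slope enters only in Aim 3. A loss of effort common to all youth is absorbed by the time trend.
- **Mitigation.** Sessions with this task are in person, and assessors are trained to use breaks and protect validity. The task is short: 252 × 2 s is about 8.4 minutes, if the interval follows the letter, so very high lapse rates are extremes. Inhibitory control is also measured by the youth- and parent-completed temperament questionnaire. These points limit the effect, but none is a scoring rule, and the plan does not say how the two measures are combined.
- **Precedent.** The cited studies may have screened for engagement. That cannot be checked here, and no such screen was carried into this plan.
- **A smaller fix.** A go-accuracy floor could be added to the existing index. That would remove the extreme cases, but omissions above the floor would still earn credit.

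**Conclusion.** The defect in the score is certain, because it follows from the stated definition: each omission is worth 0.53 points in the favorable direction, and full non-response scores 100 points better than perfect performance.

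Its consequence in this trial is not established. The lapse figures rest on assumed profiles, and their sign reverses with the type of lapse. Systematic bias in Aim 2 or Aim 3 requires omissions to track parent management or substance use. If they track neither, they add noise, which costs precision and can dilute a real association but not create one.

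This is a cheap improvement to the scoring of one task among several, and it is worth making before analysis. It is not evidence that the mediation results will be wrong.

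**What to change.** Before analysis, revise the Table 2 scoring text as follows.

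1. Make d-prime, from go hits and no-go false alarms, the inhibitory-control score for this task. State the correction for rates of 0% and 100%, and state that higher is better, since this reverses the present direction.
2. Pre-specify a minimum go accuracy as a validity rule, chosen without reference to treatment condition. Say how sessions below it are handled, and report their number by condition and visit.
3. Keep the difference index as a sensitivity analysis.
4. Do not use the commission-error rate without the go-accuracy rule, because non-response also scores best on it.

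The change needs scoring syntax and a short plan revision. It needs no new data: the present index already requires separate go and no-go accuracies, and these with the trial counts are enough for d-prime and the floor. The downside is less direct comparability with the studies cited for the index, which the sensitivity analysis partly restores.

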Anti-Coercive Problem-Solving. Teaching a parent to change his/her parent management skills requires instruction. A collaborative problem-solving approach was developed based on research indicating that parental resistance to this instruction (a high base rate phenomenon in parenting interventions) can be exacerbated or abated by therapist responses. 191 Instead of straightforward instruction, therapists are trained to demonstrate (modeling) problem-solving steps (identifying goal statements, brainstorming options, identifying manageable steps to achieve goals) and to use those steps as clinical skills to prevent or manage resistance. Problemsolving begins in the first session as therapists help parents articulate goals for their child's treatment. Parents learn to break goals into small achievable steps (behavioral chaining), and progress is tracked and praised at every session (shaping and reinforcement). Brainstorming becomes a strategy to engage parents and manage resistance. For example, if parents express doubt about their ability to complete a task, such as withholding an MVP if their youth tests positive for drugs, the therapist avoids engaging in a coercive interchange and collaboratively brainstorms solutions instead. Parents might decide to solicit assistance from another adult family member in withholding the MVP or decide to change the MVP to an item they can more confidently withhold (shaping). Thus, active problem-solving is always emphasized. Further, because behavior plans rarely work perfectly on first attempts, therapists provide strategic warnings to help parents anticipate that their plans might need revision (cueing). This approach increases parents' comfort in reporting challenges with implementing a behavior plan. Whenever this occurs, the therapist emphasizes positive aspects of the parent's effort at implementing the plan (shaping) while identifying areas for refinement, helping the parent create a new plan, and rehearsing new skills via role-play practice, as needed.

Of importance, our team's decades of clinical experience with the PMTO behavioral assessment and teaching system supports feasibility of implementing it as part of CM+. Indeed, OSLC staff implement the PDR each day with hundreds of foster parents participating in TFCO throughout the U.S., with PDR completion rates ranging from 70-100%. In addition, the behavioral assessment and teaching system is actively being utilized in programs at the OSLC outpatient clinic. As an example, for over seven years, OSLC therapists have served a population of parents referred by child welfare due to serious substance abuse and neglect of their children. As a central component of that outpatient treatment, therapists administer PDRs to parents every other day (consistent with the proposed CM+ schedule) and use the PMTO role-play and problem-solving strategies to enhance parents' delivery of effective parent management skills. OSLC staff have achieved a PDR collection

rate of 79% and a treatment completion rate of 81% with these high-risk substance-abusing parents, highlighting the feasibility of delivering these strategies in an outpatient clinic.

ACHIEVING AND ASSESSING FIDELITY. Treatment fidelity is essential for internal validity (ensuring standard family-based CM and CM+ are implemented as intended and differ from one another only with regard to the experimental enhancement). Thus, strong treatment fidelity is critical to establishing effectiveness, and a well-developed protocol will be used for training and ongoing quality assurance. Specifically, therapists in both conditions will receive training and ongoing quality assurance from [name] and [name]. The training protocol follows that used in our other family-based CM research and large-scale transport of CM to community-based practitioners. ^{35–36} An initial 3-day workshop orients clinicians to program philosophy and all intervention methods. Clinical supervision further supports therapists' implementation, modeled on a structured CM supervisory manual. ¹⁹² Following workshop training, clinicians practice treatment delivery to families and have individual supervision weekly to review progress and problem-solve barriers. As high fidelity becomes consistent, weekly phone coaching is provided, focusing on fidelity and solutions to difficult clinical problems. Bi-annual booster trainings are conducted on difficulties in fidelity or achieving clinical outcomes.

Further, therapist implementation of interventions will be measured from the perspective of the youth, parent, and therapists (via self-report) and [name] and [name] (via coding of taped treatment sessions and PDR calls). As noted, the 34-item CM Adherence Measure (CAM) was developed using Rasch methods and validated across several studies. 166 CAM subscales measure the cognitive behavioral and behavioral interventions used in CM. Using the same format, items will be created to capture PMTO enhancements in CM+. Using standard procedures employed in our other CM studies, parents and youth will complete CAMs monthly by phone (for duration of treatment) to report on therapist's CM implementation. Investigators will monitor CAMs monthly for ongoing quality assurance and as-needed therapist remediation. In addition, a more immediate fidelity assessment and remediation mechanism will be therapists completing CAMs after each session and phone call to report on their own behavior. Further, therapists will record all treatment sessions and phone calls. [name] and [name] will complete observational ratings 167,193 on randomly selected (20%) treatment sessions and (20%) calls. Employing procedures used successfully in Azrin et al. 129 to monitor and improve fidelity, ratings will be compared to therapist report from the same session/call. Inconsistencies between therapist self-report and observational ratings will trigger remediation training and more intensive supervision. Session/call notes and reports also will be evaluated weekly to ensure fidelity across conditions.

BALANCING THERAPIST CHARACTERISTICS ACROSS CONDITIONS. We anticipate that 3 therapists will deliver CM, and 3 different therapists will deliver CM+. Prior to beginning youth recruitment, therapists will be randomized to provide services in either the CM or CM+ conditions. To minimize bias, therapists will be balanced as much as possible, given the small sample, by age, sex, race, and years of experience.

ADDRESSING RISK OF CONTAMINATION. Both treatment arms are conducted within a clinic, raising concerns of potential contamination between therapists in the same clinic. Nevertheless, based on our experience conducting RCTs, we view this risk as low. Indeed, CM and the PMTO enhancements are highly structured, requiring initial training and supervision specific to identifying barriers to treatment fidelity. Across numerous trials for similar interventions, we have found therapist fidelity varies. 194-196 More generally, research indicates even experienced therapists revert to prior/usual practice in the absence of formal structures such as ongoing supervision. 36 Thus, it is unlikely that a standard CM therapist who inadvertently hears about PMTO strategies would be able to implement them with fidelity, especially in the absence of training or access to materials and supervision. Nevertheless, contamination risk will be mitigated in several ways. First, therapists deliver treatment in only 1 condition. Second, only therapists within the condition have access to resources to facilitate implementation. Third, clinical supervision is conducted individually, not in groups. Fourth, therapists formally agree not to discuss CM and CM+, except with therapists in the same condition. Fifth, as described, we measure implementation in both conditions, allowing close monitoring for potential contamination during the trial. Any evidence of contamination will be addressed immediately with therapists.

DATA ANALYSIS STRATEGY

The design leads to 11 measurements of the direct target (parent management; level-1), 6 measurements of indirect targets (behavioral regulation, peer relations; level-1), and 6 measurements of ultimate outcomes (substance use, externalizing behavior; level-1) nested within 172 youth/parents (level-2). Analyses will use latent growth curve formulations of mixed-effects regression models. These highly flexible models accommodate variability in number and spacing of measurements, discrete (i.e., urine drug screens [UDS]) and continuous (i.e., parent management, behavioral regulation, peer relations, GAIN scores, externalizing behavior) outcomes, and separate patterns of change for distinct phases (i.e., during- and post-treatment).

EXPERIMENTAL MEDIATION AND CAUSAL INFERENCE. The experimental mediation design emphasizes evidence supporting causal inferences, and there are important conceptual and statistical considerations. As reviewed by [name], ¹⁹⁹ by randomizing youth/parents, the effect of CM+ on parent management is a causal estimate. However, the effect of parent management on drug use and externalizing behavior is not straightforwardly causal, it is potentially influenced by unmeasured confounding variables. Following [name]'s

recommendations, and to support causal inferences, this is addressed in 3 ways. First, the enhancement design directly targets the mediator—increasing probability of a causal effect between mediator and outcome. Second, longitudinal measurements of the mediator and outcomes address temporal sequencing—demonstrating that mediator effects occur before outcome effects. Third, supplemental models evaluate confounding variables—providing evidence that mediator effects are not due to confounders.

MODEL FORMULATION. The underlying model is a mixed-effects latent growth curve model with repeated measurements (level-1) nested within youth/parents (level-2), implemented in Mplus (v7.31;¹⁹⁷). As reviewed by [name],²⁰⁰ there are several options for modeling longitudinal mediation. Flexibility of growth models for targeting phase-specific change²⁰¹ are leveraged and combined with parallel process models for mediation.²⁰² In a single model, there are separate change estimates for during- and post-treatment phases, directly addressing temporal sequencing of mediators and outcomes. The UDS outcome is modeled using a Bernoulli distribution, and remaining ultimate outcomes, direct targets, and indirect targets are modeled with normal distributions. Time terms are computed using assessment dates.²⁰³ Treatment condition is a youth/parent-level predictor (level-2; CM = 0, CM+ = 1), and cross-level interactions are specified between condition and level-1 growth and phase terms. Models, as indicated, control for age, sex, race, ethnicity, SES, and treatment history. Likewise, preliminary models test, and control, for differences in outcomes across therapists and clinics. Follow-up models determine whether individual paths and mediated effects differ for males and females.

STATISTICAL TEST FOR MEDIATION. The test for mediation is based on the product of coefficients (i.e., $\alpha\beta$) with asymmetric bootstrapped *SE*s and 95% CIs for the product.²⁰⁴ This test requires estimation of two parameters and their *SE*s, where, for example, α is the effect of CM+ on parent management and β is the effect of parent management on substance use and externalizing behavior. Parameters are obtained from Mplus and supplied to PRODCLIN²⁰⁵ for the asymmetric boostrapped *SE*s and CIs. This approach offers enhanced statistical power²⁰⁶ and applies both to multilevel data²⁰⁷ and longitudinal mediation.²⁰⁰

EVALUATION OF SPECIFIC AIMS

AIM 1: DETERMINE WHETHER PARENT MANAGEMENT SKILLS (DIRECT TARGET) MEDIATE THE EFFECT OF TREATMENT ON YOUTH SUBSTANCE USE & BEHAVIOR PROBLEMS (ULTIMATE OUTCOMES). The test for mediation requires the coefficient and SE for CM+'s effect on parenting (a-path) and parent management's effect (controlling for treatment) on substance use and externalizing behavior (b-path). Of note, a preliminary model evaluates the direct effect of CM+ on substance use and externalizing behavior (c-path), though as noted by [name], ¹⁹⁹ mediation should be tested regardless of this path's significance.

a-path. This model is specified with 11 repeated measurements of parenting as the outcome. To address temporal sequencing, the model estimates separate change rates for during- and post-treatment phases. This is tailored to each youth's course of treatment using coding strategies for discontinuous (piecewise) change (see Singer and Willett²⁰¹). Changes during treatment phase are modeled with linear and quadratic terms for number of months since baseline. A dichotomous phase indicator differentiates post- and during-treatment measurements, and post-treatment change is modeled as linear and quadratic terms for number of months since treatment end. This provides three estimates: during-treatment slope (estimate of interest for mediation test), overall shift in parenting levels from during- to post-treatment, and post-treatment slope.

b-path. This model is more complex, simultaneously evaluating the mediator and outcome processes. To obtain this coefficient, the a-path is modeled along with the outcome model (c-path; testing for differences between CM+ and CM on substance use and externalizing behavior). With fewer outcome measurements, the model includes a during-treatment slope term and indicators to differentiate 9- and 12-month assessments, providing three estimates: during-treatment slope, change at 9 months, and change at 12 months. To obtain the b-path coefficient, a regression is specified with *during-treatment mediator slope* as a predictor of *outcome at 9 and 12 months*. This provides a targeted test of mediation, with during-treatment change in the mediator as a predictor of post-treatment outcomes.

Ethnicity effects. In close consultation with project consultant [name], and to address potential for differential effects across project clinics, formal moderated mediation tests can be performed.²⁰⁸⁻²⁰⁹ These tests determine whether observed mediation effects differ for Latino and non-Latino youth/parents. Sample size means that results are hypothesis-generating and thus will focus on estimation of confidence intervals. The same approach will be used to evaluate moderated mediation for ethnicity in Aims 2 and 3.

Confounding variables. Although randomization, the enhancement mediation design, and models addressing temporal sequencing increase the likelihood of valid causal inferences for mediation, a remaining assumption is that there are no unmeasured confounding variables for the mediator's effect. Cox et al.²¹⁰ recommends sensitivity analyses for confounder bias be used. First, VanderWeele's²¹¹ formulas identify youth/parents with the same value on the mediator but different values on the outcome, as well as youth/parents with the same value on the mediator across both CM and CM+ groups. Second, residuals from the models just detailed should be uncorrelated, and Mplus code from Imai et al.²¹² is used to determine whether the mediated effect differs based on unmeasured pre-treatment variables. Third, Mauro's²¹³ correlational method evaluates the sources of error variance from the mediation model, determining how large the effect of an omitted variable

would need to be to negate the mediated effect.

AIM 2: DETERMINE WHETHER PARENT MANAGEMENT SKILLS (DIRECT TARGET) MEDIATE THE EFFECT OF TREATMENT ON YOUTH BEHAVIORAL REGULATION & DEVIANT PEER RELATIONS (INDIRECT TARGETS). In the parallel process model for Aim 2, the *a-path* is identical to that for Aim 1. The "outcome" model is nearly identical, the only difference being that the "outcomes" are indirect targets of treatment, behavioral regulation and peer relations. The b-path coefficient represents the association between the during-treatment slope for parent management and the 9- and 12-months post-treatment levels of behavioral regulation and peer relations.

AIM 3: DETERMINE WHETHER BEHAVIORAL REGULATION & DEVIANT PEER RELATIONS (INDIRECT TARGETS) MEDIATE THE EFFECT OF PARENT MANAGEMENT SKILLS (DIRECT TARGET) ON YOUTH SUBSTANCE USE & BEHAVIOR PROBLEMS (ULTIMATE OUTCOMES). Aim 3 uses the same approach, with one key difference: rather than treatment condition, the initial variable is parent management (the direct target of treatment) and, as such, there are repeated measurements. The *a-path* represents the effect of parent management on behavioral regulation and deviant peer relations. With both measured longitudinally, this takes the form of the during-treatment slope for parent management predicting the during-treatment slope for behavioral regulation and deviant peer relations. Although this could confound timing and sequencing of a-path effects, the results of Aim 2 will have established the extent to which there is evidence supporting a causal association between the direct and indirect targets of treatment. The outcome model is identical to that for Aim 1. The *b-path*, holding constant the effect of parent management, is the effect of the during-treatment slopes for behavioral regulation and peer relations on the post-treatment levels of substance use and behavior problems.

STATISTICAL POWER FOR MEDIATED EFFECTS. The proposed mediation models include estimates of: (1) the effect of the initial variable on the hypothesized mediator (α-path), (2) the effect of the hypothesized mediator on the outcome (β-path), and (3) the mediated effect (αβ). Using Monte Carlo simulations implemented in Mplus, $^{214-215}$ power is determined by the percentage of replications with a significant effect for the path of interest. Using covariance algebra provided by Thoemmes et al., 215 parameters (path coefficients, variances, residuals) were tailored to reflect α- and β-paths with small-to-medium ($R^2 = .07$) effects. For each model, sample size, conservatively assuming 10% attrition, was 155, with 10000 replications from the population. For a-path, power was >.90 to detect a small-to-medium effect of the initial variable on the mediator. For β-path, power was .85 to detect a small-to-medium effect of intermediate targets on ultimate outcomes. For the mediated effect, power was .83. This estimate is conservative due to the simulation's Sobell *SE* method. As an upper bound on power, and based on simulations using the proposed asymmetric *SE* method, Fritz and MacKinnon²¹⁶ found a sample of *N*=74 sufficient for .80 power to detect medium effects for α- and β-paths.

ATTRITION AND MISSING DATA

Participants will be retained in research measurement independent of CM/CM+ participation following intent-to-treat principles.²¹⁷ Along with this, the successful participant tracking and retention protocols used in OSLC research will minimize missing data. However, because some data will inevitably be missing, methods recommended by Schafer and Graham²¹⁸ will evaluate assumptions and guide analyses. Three steps will be used: (1) For a small proportion of missing data with evidence of Missing at Random (MAR), data will be analyzed using the estimation procedures described above. (2) For a non-trivial amount of missing data and evidence of MAR, multiple imputation for repeated measurements will generate complete data.²¹⁹ (3) For a non-random missing data mechanism, pattern mixture models will identify and control its effects.^{203–204}

BIBLIOGRAPHY & REFERENCES CITED

- 1. [name], P., & Reid J. (1987). Parent observation and report of child symptoms. *Behavioral Assessment*, 9, 97-109.
